The new questionnaire consists of 38 questions on an individual's dietary intake across 17 product groups. The questionnaire and cutoff values are based on the Guidelines for Healthy Diet (Kromhout et al., 2016), where applicable further refined using the recommendations of the Netherlands Nutrition Centre. After completing the questionnaire, a profile wheel (see Figure 1) is displayed, providing insight into compliance with the guidelines for 17 product groups. In this profile wheel, a “traffic light” color is used for each product group to indicate whether an individual roughly meets the guidelines (green), consumes more than 50% of the recommended amount (orange), or consumes less than 50% of the recommended amount (red). For (sub)product groups for which no guideline exists, a grey color is shown (for example, for potatoes).

[figure not shown]

Figure 1. Example of a “Profile wheel” for an individual after filling out the Nutri-plus module.

The product groups defined by the Health Council were further refined to provide participants with more detailed insight into areas of their dietary pattern that could be improved. In addition, unhealthy choices are included in the Nutri+ module, even though they are not part of the Guidelines for Healthy Diet (Gezondheidsraad, 2015). By assessing and displaying these in the profile wheel, individuals can also gain insight into the extent of their unhealthy choices.

With the Nutri+ module, we aim to offer a dietary intake assessment as an integral part of the 360-degree tool, enabling individuals to gain insight into their own dietary patterns and areas for improvement. These outcomes can be used to provide personalized dietary advice or interventions tailored to the individual.

Before the Nutri+ module can be used for personalized dietary assessment and advice, it must be evaluated to determine whether it provides an accurate picture of an individual's dietary intake. To this end, the outcomes of the Nutri+ module, consisting of a red–orange–green categorization, can be compared with those of an already validated method for dietary intake assessment. In the literature, (weighed) dietary recall methods are commonly used to validate dietary questionnaires (Cade, 2002), as these methods are less sensitive to underreporting than food frequency questionnaires (Prentice, 2011).

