In a 24-hour recall method, individuals are asked to provide detailed information about all foods and beverages consumed in the previous 24 hours (Meijboom, 2017). To obtain a reliable estimate of habitual dietary intake, the 24-hour recall must be repeated on multiple days in order to correct for day-to-day variation. Wageningen University & Research has developed and validated a Dutch online 24-hour dietary recall method that can be completed entirely online by participants, known as “Compl-Eat” (Meijboom, 2017). This significantly reduces the costs and burden for both researchers and participants.

This study will consist of two phases. The first phase will involve a pre-test to assess the usability, comprehensibility, and completeness of the developed Nutri+ module among end users and experts. The insights generated will be used to further improve the Nutri+ module and the profile wheel visualization. After completion of the first phase, the second phase will commence, in which the Nutri+ module will be compared with a reference method in an evaluation study. The selected reference method for this evaluation study is a 24-hour recall using Compl-Eat.

2 Goal

Goal of the Nutri+ module: To assess, at the individual level, the extent to which a person complies with the dietary guidelines and where there is room for improvement. These insights are used to provide personalized dietary advice and to monitor an individual's dietary intake.

Phase 1: Pre-test

Objectives

- To gain insight into the user experiences of the target group with completing the questionnaire and with regard to the visualization of the profile wheel.
- To collect feedback from experts on the Nutri+ module (including completeness, question formulation, example products, etc.).
- To use the collected user insights and expert feedback to further improve the Nutri+ module and the profile wheel visualization before starting the second phase of the study (the evaluation study).

Phase 2: Evaluation study

Main objective: To evaluate whether the absolute intake in grams, as measured by the Nutri+ module, is comparable to Compl-Eat for the 21 product groups. This will be explored both quantitatively (e.g., what percentage of intake is covered by the Nutri+ module compared with Compl-Eat) and qualitatively (e.g., where the differences between Compl-Eat and the Nutri+ module lie). These insights can be used to further improve the tool.

Sub-objectives:

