- To investigate whether the results of the Nutri+ module are reproducible over time or whether time effects are present, with a correlation coefficient of ≥ 0.75 between two measurement points considered successful.
- To evaluate the Nutri+ module (dietary questionnaire) against the Compl-Eat 24-hour recall method. Specifically, we aim to examine whether the Nutri+ module can accurately classify at least 75% of individuals into three categories for the 21 product groups.
- To evaluate the visualization of the profile wheel by users of the Nutri+ module.

3 Study design

This is a longitudinal randomized study to evaluate the Nutri+ dietary intake module. The Nutri+ module can be completed by participants at home via an online portal; it is filled out only once and takes approximately 30 minutes to complete. As a reference method, Compl-Eat is used. This is an online 24-hour recall method developed by Wageningen University & Research (Meijboom et al., 2017). Participants in the study can complete this 24-hour recall themselves at home via a portal, recording everything they ate and drank in the previous 24 hours. Based on the submitted data, the Compl-Eat platform can determine for an individual how much and what was consumed at both the product group and individual product levels. Compl-Eat is completed by participants on four non-consecutive days—three weekdays and one weekend day (Saturday or Sunday)—to obtain an accurate representation of an individual's average intake. The 24-hour recalls are manually checked for completeness by a researcher afterwards.

A randomized cross-over design is used, in which one group of participants completes the Nutri+ module first, while the other group completes Compl-Eat first. The days on which participants complete

the Nutri+ questionnaire and the days on which Compl-Eat is completed are randomly selected. There is a minimum interval of 7 days between the Nutri+ module and the first or last day of Compl-Eat.

In addition, possible time effects in dietary recording and the reproducibility of the Nutri+ module results are examined. To this end, participants are invited again after three to six months to repeat the entire procedure of completing the Nutri+ module once and Compl-Eat four times. The first series of questionnaires is sent out in April; the second series begins in September.

See Figure 2 for a schematic overview of the study design.

[figure not shown]

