The second phase involves recruiting participants through social media campaigns and the completion of the Nutri+ module and Compl-Eat. Participants are recruited via social media advertisements, which link them to an online information sheet. After reading the information sheet, participants can provide online informed consent for participation in the study. They are then automatically directed to an online screening questionnaire (see inclusion and exclusion criteria). This screening questionnaire automatically assesses whether the individual meets the study's selection criteria. Candidates who do not meet the criteria are informed immediately. Candidates who do meet the criteria are directed to a baseline questionnaire to collect various baseline data (medication use, physical activity, adherence to any dietary or nutritional rules, and allergies or intolerances). Participants are then informed about the further study schedule and procedures.

The study uses a cross-over design, in which participants are randomly assigned to one of two sequences: starting with the Nutri+ module or starting with Compl-Eat. Participants who start with the Nutri+ module during the first series (autumn 2022) will start with Compl-Eat during the second series (spring 2023), and vice versa.

For all participants, the days on which the Nutri+ module and Compl-Eat must be completed are randomly selected. Both the Nutri+ module and Compl-Eat are completed at home using login credentials for the respective online platforms. Participants are not informed of the full schedule in advance to minimize potential influence on their dietary behavior. One day before a participant's first "assessment day," they are contacted by email by a researcher, requesting that they complete either the Nutri+ module or Compl-Eat the following day. Participants can respond to this email if the scheduled day does not fit their personal planning. In that case, the researcher reschedules the assessment day, and the participant is contacted again at a later time.

During the first series (autumn 2022), all participants complete Compl-Eat on four days within a two-week period and complete the Nutri+ module once. A minimum interval of seven days is maintained between completing Compl-Eat and the Nutri+ module to prevent interference between the methods.

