After completing the first series (autumn 2022), participants are reminded that they will be contacted again in spring 2023 to complete the Nutri+ module and Compl-Eat. The same procedures are followed in spring 2023 as in autumn 2022.

Participants are also asked to complete an evaluation questionnaire regarding their experiences with completing the questionnaire and the visualization of the dietary profile wheel.

After data collection for the evaluation study is completed, the data are analyzed. Based on this analysis, recommendations will be made for adjusting the Nutri+ module (questionnaire, algorithms, and cut-off values) and for improving the visualization of the profile wheel.

Tabel 2: Overview timeline and investment for participants evaluation study

	How often and when	Total time investment
--	--------------------	-----------------------

Nutri+ module	1 time filling out autumn 2022 1 time filling out spring 2023	2 times, 20 minutes. 40 minutes in total.
Compl-eat	1 time 4 days filling out autumn 2022 1 time 4 days filling out spring 2023	80 minutes per time. 160 minutes in total.
Evaluation questionnaire	1 time filling out	15 minutes

6 Outcome variables

To evaluate the Nutri+ module in comparison with Compl-Eat, it is first necessary to assess the extent to which the food groups used in the Nutri+ module are also available in Compl-Eat. The outcomes listed below depend on the results of this mapping. In addition, Compl-Eat will need to apply the same food group classification based on the same cut-off values per product group as used in the Nutri+ module.

Primary outcomes

- Intake in grams for the 17 product groups that are quantitatively assessed (Fruit, Vegetables, Legumes, Nuts and Seeds, Fish, Dairy, Meat, Eggs, Soft Drinks, Alcohol, Coffee, Tea, Snacks, Sweet Spreads, Chips/Nuts/Party Snacks, Fast Food, Desserts/Ice Cream/Cakes) for both Compl-Eat and the Nutri+ module.

Secondary outcomes

- Evaluation overall and by subgroup (sex, BMI, etc.) for all product groups available in both Compl-Eat and the Nutri+ module, for which guidelines exist to assess reproducibility and classification. For Nutri+, these include: Fruit, Vegetables, Butter and Cooking/Frying Products, Dressings and Oils, Legumes, Nuts and Seeds, Fish, Dairy, Meat, Eggs, Cereal Products, Potatoes, Soft Drinks, Alcohol, Coffee, Tea, Snacks, Sweet Spreads, Chips/Nuts/Party Snacks, Fast Food, Desserts/Ice Cream/Cakes.
- Energy intake based on Compl-Eat

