- Expected energy intake based on sex, age, weight, and physical activity
- Evaluation of the profile wheel

7 Description of incidents, safety, adverse events, side effects

The study for participants consists of completing dietary questionnaires and 24-hour dietary recalls. Due to the nature of the study, no incidents or adverse events are expected. Any complaints regarding the conduct of the study, the websites used, or other questions or remarks can be submitted via email or telephone, as indicated in the participant information.

8 Data-analysis and statistics

For Compl-Eat, all analyses will be based on the average intake per product group across the four assessment days within a single measurement series (spring or autumn).

Based on the Compl-Eat data, it will be assessed whether there is excessive under- or over-reporting in the study population. To this end, the number of calories consumed, as calculated by Compl-Eat, will be compared with the expected caloric intake based on participants' age, sex, height, and weight.

The agreement between classifications in Compl-Eat and the Nutri+ module will be evaluated by assessing the percentage overlap in categorization and subsequently examining correlations between the scores. The goal is for 75% agreement per product group between the Nutri+ module and Compl-Eat. If lower agreement is observed, the data will be qualitatively examined to identify areas for improvement in the Nutri+ module.

In addition, the intake in grams per product group as measured by the Nutri+ module and Compl-Eat will be examined. Correlation coefficients will be calculated to assess agreement between the Nutri+ module and Compl-Eat. These outcomes are primarily exploratory and aim to provide insight into where the largest differences between Compl-Eat and Nutri+ occur. These insights can be used to further improve the Nutri+ module.

To assess the reproducibility of the Nutri+ module, correlations between the spring and autumn measurements will be used.

Participants' opinions on the visualization of the profile wheel will be evaluated using descriptive information.

9 Risk analysis relating to the conduct of the study

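### The uncorrected four-day Compl-Eat mean can pull agreement below 75% even for an error-free Nutri+, and the plan cannot tell that noise from tool error

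*Combined protocol and SAP*

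**What the plan says.** The introduction accepts that one recall day is not enough: "the 24-hour recall must be repeated on multiple days in order to correct for day-to-day variation". Repetition is the only correction offered. Section 3 sets four non-consecutive recall days, three on weekdays and one at the weekend, and section 5 adds that "all participants complete Compl-Eat on four days within a two-week period". Section 8 then fixes the reference value: "all analyses will be based on the average intake per product group across the four assessment days within a single measurement series".

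The colour rule in the introduction is green for roughly meeting the guideline, orange for more than half of the recommended amount, and red for less than half. Section 6 carries the rule over to the reference: "Compl-Eat will need to apply the same food group classification based on the same cut-off values per product group". The sub-objective in section 2 is that Nutri+ "can accurately classify at least 75% of individuals into three categories for the 21 product groups". Section 8 repeats the target by group: "The goal is for 75% agreement per product group between the Nutri+ module and Compl-Eat".

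If a group falls short, section 8 provides for a qualitative look at the data to find improvements to Nutri+. Section 5 says that the results will lead to recommendations on the questionnaire, algorithms and cut-off values. The plan contains no usual-intake model, no de-attenuated correlation and no separate reading of the target for foods eaten occasionally, although fish, legumes, nuts and seeds, and eggs are on the list in section 6.

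**The concern.** A mean of four days estimates a person's usual intake with error. For a food eaten about once a week the error is large: the four days either miss the food or overstate it. A person whose usual intake is near a cut-off can then land in the wrong colour on the reference side even when Nutri+ is exactly right. The same noise lowers the correlations in grams, which serve the primary outcome.

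The size of this effect differs by product group, but the goal is 75% for all of them. A low figure for one group could reflect a poor Nutri+ question or simply too few recall days, and the planned analyses do not separate the two. Because reference error is never named as a possible cause, a sound question or cut-off could be changed for the wrong reason.

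**Working it through.** **The plan's own figure.** The 75% goal comes without a derivation or variance inputs, so there is nothing to reproduce. The check asks instead what agreement an error-free Nutri+ would reach.

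**Inputs from the documents.** Four recall days per series; three weekdays and one weekend day, non-consecutive, within two weeks; cuts at 100% and 50% of the recommended amount.

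**Inputs that are assumptions.** Guideline amounts of 1 or 2 portions a week, eating frequencies, portion variability and variance ratios. The documents give none of these.

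**Step 1: a person who eats the food once a week.** Suppose one eating day falls at random in each week, and *a* of the four recall days are in week 1 and *b* = 4 - *a* in week 2. Then P(no eating day recalled) = (7 - *a*)(7 - *b*)/49.
- 2 and 2 days: 25/49 = 0.51.
- 3 and 1 days: 24/49 = 0.49.
- 4 and 0 days: 21/49 = 0.43.

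Averaged over the 182 permitted schedules in a 14-day window that starts on a Monday, the probability is 0.50. It is 0.48 if the food is always eaten on the same weekday. With independent days it is (6/7)^4 = 0.54.

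**Step 2: what four days can show.** With identical portions, *k* eating days give 7*k*/4 portions a week: 0, 1.75, 3.5, 5.25 or 7.
- Guideline 1 a week, true intake 1 a week (green), independent days: red with probability 0.54, green with 1 - 0.54 = 0.46. Orange would need a value from 0.5 to 1, and none exists.
- If portions vary with an assumed CV of 30-50%, a single eating day falls in orange about 4-16% of the time.
- Guideline 2 a week, true intake 2 a week (green): at least two eating days are needed. 1 - (5/7)^4 - 4(2/7)(5/7)^3 = 1 - 0.260 - 0.416 = 0.32.

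**Step 3: agreement in a group with a perfect Nutri+.** Each person's true weekly frequency *f* is drawn from a gamma distribution (shape 1-8). Recalled eating days are Binomial(4, *f*/7), portions are identical, and Nutri+ is set equal to *f*.

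| Assumed guideline | Assumed mean intake | Agreement, 4 days |
|---|---|---|
| 1 a week | 0.5-2 a week | 29-69% |
| 1 a week | 0.25 or 5 a week | 79-96% |
| 2 a week | 1-3 a week | 44-69% |

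A second model, with beta-distributed eating probability and a portion CV of 40%, gives 51-77% (guideline 1, mean 1) and 48-70% (guideline 2, mean 2). Far from the cut-offs it gives 82-92% (guideline 1, mean 0.25) and 92-97% (guideline 1, mean 5).

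**Step 4: eight days instead of four.** In the second model the first two ranges become 57-79% and 55-74%. More days help, but do not secure 75%.

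**Step 5: correlations.** If the within- to between-person variance ratio is λ, the correlation of true intake with a four-day mean is 1/√(1 + λ/4). For λ = 1, 2 and 4 this is 0.89, 0.82 and 0.71.

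**The case against.** The strongest reply is that 75% is a goal and not a test. Missing it leads to a qualitative look at the data, classification is a sub-objective and a secondary outcome, and section 8 calls the gram comparison primarily exploratory. Section 2 also asks where the two methods differ, so an attentive analyst could notice recall days with no intake. This stands as a limit on the consequence: no formal conclusion fails. It does not remove the problem, because the only stated purpose of looking at a shortfall is to improve Nutri+, and no planned output would show how much of the shortfall comes from the reference.

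A second reply is that the per-series mean is there for a reason: the comparison over time needs one value per series. That is correct, and the mean should not be dropped.

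A third is that the documents give no intake distributions or guideline amounts, so nobody can say which groups are affected. That also stands. A reader might infer that a perfect Nutri+ is bound to miss 75% for every food not eaten daily. The documents do not support this, since the ceiling exceeds 75% when most people are far from the cut-offs. A reader might also infer that orange can never occur for a weekly food. That needs identical portions, whereas the study measures grams. Fast food is a weak example, because the introduction says that unhealthy choices are not part of the guidelines.

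**Conclusion.** The point holds as a matter of what could happen and what the plan could not detect. The reference category is an uncorrected four-day mean. For product groups not eaten daily with usual intake near the cut-offs, agreement for an error-free tool could lie well below 75%: about 29-69% under the gamma assumptions with a guideline of one portion a week. Far from the cut-offs it is about 79-96%. Only the figures for a once-weekly eater (0.50, or 0.54 with independent days) follow from the recall schedule once the eating frequency is set. The group percentages rest on assumed guidelines and distributions, and their spread is itself the reason why one flat target is hard to read.

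Attenuation of the gram correlations applies to every group with day-to-day variation, to a degree that the recall data can show. The reproducibility criterion of 0.75 compares Nutri+ with itself, so this point does not touch it. The change is a cheap improvement: the data can still be interpreted, provided that the reference noise is reported.

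**What to change.** Keep the per-series mean for the time-effect aim, and add two items to section 8.

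1. Per product group, estimate within- and between-person variance from the recall days, either within each series or across both with a season term. Report de-attenuated correlations (crude correlation × √(1 + λ/4)) beside the crude ones.
2. Per product group, report the agreement that a perfect tool would reach given that variance. Read the 75% goal against this figure before any Nutri+ question, algorithm or cut-off is changed.

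For groups with zero intake on most recall days, a two-part usual-intake model (whether eaten, and how much) on all eight days is an option. Pooling the eight days without a model is not a substitute.

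The cost is analysis work only: no new data and no added burden for participants. De-attenuated estimates have wider intervals. They also correct only for random day-to-day variation, and not for reporting errors that the two instruments share.

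### The 75% agreement goal ignores the order of the colours and sets no limit on red-green reversals, so a product group can meet it with up to 25% of users in opposite categories

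*Combined protocol and SAP*

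**What the plan says.** The introduction defines the colours of the profile wheel as an ordered scale. Green roughly meets the guideline; otherwise a person "consumes more than 50% of the recommended amount (orange), or consumes less than 50% of the recommended amount (red"). Section 2 gives the purpose at the level of the individual: "These insights are used to provide personalized dietary advice and to monitor an individual's dietary intake".

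The classification sub-objective in Section 2 reads: "we aim to examine whether the Nutri+ module can accurately classify at least 75% of individuals into three categories for the 21 product groups". Section 8 puts this into practice by "assessing the percentage overlap in categorization and subsequently examining correlations between the scores". The mark is "The goal is for 75% agreement per product group between the Nutri+ module and Compl-Eat", and the consequence of missing it is: "If lower agreement is observed, the data will be qualitatively examined to identify areas for improvement in the Nutri+ module".

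The documents attach no threshold to the correlations between the two methods. The one correlation mark they give, "with a correlation coefficient of ≥ 0.75 between two measurement points considered successful", concerns repeat administrations of Nutri+ over time. They plan no weighted agreement statistic, no count of opposite-colour results and no limit on them.

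**The concern.** Percentage overlap has only two outcomes, match and mismatch. On an ordered scale used for individual advice, mismatches differ in weight. Orange instead of green shifts the advice by a step. Green instead of red tells a person that no change is needed where the reference shows the largest shortfall, and the reverse error does the opposite.

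Because the goal does not separate the two, a product group could meet it while a noticeable share of users get the opposite colour. The review that Section 8 attaches to the goal would then not start for that group. At stake is whether the classification goal reflects the use for which the module is being evaluated.

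**Working it through.** **Inputs.** From the documents: 75% per product group (Sections 2 and 8); three ordered colours (introduction); the same cut-offs applied to both methods (Section 6); Compl-Eat intake averaged over four days (Section 8); 200 participants (Section 4). The 75% is a chosen target without a derivation, so there is no plan figure to reproduce. The documents give no expected colour distribution, so every joint distribution below is an assumption.

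**1. What the goal allows.** Let E, A and O be the shares with exact, one-step and opposite colours, with E + A + O = 100%. E ≥ 75% requires only A + O ≤ 25%.
- With A = 0, O can reach 25%, which is 50 of 200 participants.
- With O = 0, the goal is missed only if A exceeds 25%, which is more than 50 of 200.

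**2. What the statistic cannot see.** Two constructed tables, n = 200 (rows Compl-Eat red, orange, green; columns Nutri+ in the same order):
- Table A: [48, 0, 20], [0, 64, 0], [20, 0, 48]. Agreement 160/200 = 80%; opposite 40/200 = 20%; one-step 0%.
- Table B: [54, 13, 0], [13, 40, 13], [0, 13, 54]. Agreement 148/200 = 74%; one-step 52/200 = 26%; opposite 0%.

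Quadratic-weighted kappa = 1 − (observed mean squared distance)/(distance expected from the margins).
- A: 1 − (0.20 × 4)/1.36 = 0.41.
- B: 1 − (0.26 × 1)/1.34 = 0.81.

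Unweighted kappa = (observed − chance agreement)/(1 − chance agreement).
- A: (0.80 − 0.3336)/(1 − 0.3336) = 0.70.
- B: (0.74 − 0.3334)/(1 − 0.3334) = 0.61.

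Percentage overlap and unweighted kappa both favour A, and weighted kappa favours B. Correcting for chance alone therefore does not address the point. With true agreement of 80%, P(Binomial(200, 0.80) ≥ 150) = 0.97, whatever the type of error. These tables show a property of the statistic; they are not forecasts.

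**3. Smoothly distributed intake.** Assume bivariate-normal intake, equal margins and the same cut-offs in both methods, with red and green equally common. Choose the correlation that gives the stated agreement and read off the opposite share:

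| Users in orange | Agreement | Opposite colours |
|---|---|---|
| one third | 80% | about 0.06% |
| one third | 75% | about 0.3% |
| 20% | 75% | about 2% |
| 10% | 75% | about 9% |

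**4. Foods eaten now and then.** Assume a guideline of one portion a week, a share w of participants who eat exactly that and the rest none, independent days, and a Nutri+ module without error.
- A weekly eater has no portion on any of the four recall days with probability (6/7)^4 = 0.540. Compl-Eat then gives red and Nutri+ green.
- One portion in four days averages 7/4 = 1.75 a week, which is green. Orange is empty.
- Opposite share = 0.540 × w. With w = 20% it is 10.8% (agreement 89.2%). With w = 40% it is 21.6% (agreement 78.4%), and the goal is met with probability about 0.89 at n = 200.

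In this illustration every reversal comes from the four-day reference and runs in one direction. The 75% goal shows neither fact.

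**The case against.** The strongest reply is that large reversal rates are improbable. Both methods cut an intake quantity at the same points and orange lies between red and green, so error that jumps over orange without ever landing in it is not credible for most groups. Step 3 bears this out, and for such groups a limit of several per cent would seldom bind. This stands for smooth intakes. It does not extend to groups with many zeros; fish and legumes, both listed in Section 6, may behave as in step 4.

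The second reply is that the plan would see the problem by other routes. Section 8 examines correlations between the scores, which here would be 0.41 for table A and 0.81 for table B. It also compares grams per product group to locate the largest differences. The main objective in Section 2 explores gram differences both quantitatively and qualitatively, and none of this depends on missing 75%. A reader might infer that errors in a group that meets the goal go unexamined; the documents do not support that. What remains is that these analyses have no threshold and no part in the classification goal or its review trigger.

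Third, the 75% is a descriptive goal under a sub-objective. It is not a formal test, and missing it leads only to a closer look at the data. Under Section 5, recommendations follow from the analysis as a whole. This also stands, and it limits the consequences.

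**Conclusion.** The point holds as a gap in the classification goal. The goal is blind to the distance between colours, and the bound of 25% opposite colours follows from its definition with no further assumption. How much of that bound is used depends on the food group: about 0.06% to 9% at 75-80% agreement under the bivariate-normal assumptions, and 10.8% to 21.6% in the episodic illustration with 20% to 40% weekly eaters. The documents do not allow a choice within these ranges.

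A reader might go further and infer that the rule will in practice approve a module that reverses a fifth of users' colours and reject one with only one-step errors. The documents do not support that. A fifth reversed with no one-step errors is a constructed extreme. A module with only adjacent errors misses the goal only if those errors exceed 25% of users, and missing it means review, not rejection.

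**What to change.** In Section 8, keep the 75% goal and add, for each product group:

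- the percentage of participants in opposite categories, reported separately for Nutri+ green with Compl-Eat red and for the reverse;
- weighted kappa, with the weights stated in advance;
- a second trigger, so that the qualitative review starts when agreement is below 75% or the opposite-category share exceeds a limit that the sponsor fixes before analysis.

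The cost is a few lines of wording and two cells of a table that the agreement analysis already needs; no new data are required. The downside is that some groups that meet 75% will also be reviewed. The limit itself is a judgement that the documents do not supply, so the sponsor should give a reason for the value chosen.

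### The single 75% raw-agreement goal is not corrected for chance, so it sets a different standard in each product group depending on how the colours are distributed

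*Combined protocol and SAP*

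**What the plan says.** One of the sub-objectives in Section 2 is to see whether the module "can accurately classify at least 75% of individuals into three categories for the 21 product groups". Section 8 repeats this as a target for each group: "The goal is for 75% agreement per product group between the Nutri+ module and Compl-Eat". The statistic is described there too: agreement "will be evaluated by assessing the percentage overlap in categorization and subsequently examining correlations between the scores".

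The colours are not quantiles of the sample. The introductory description of the profile wheel defines them by fixed fractions of the recommended amount: roughly meeting the guideline, above half of it, or below half of it. Section 6 carries the same limits over to the reference method: "Compl-Eat will need to apply the same food group classification based on the same cut-off values per product group".

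Missing the target has one stated consequence in Section 8: "If lower agreement is observed, the data will be qualitatively examined to identify areas for improvement in the Nutri+ module".

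Kappa, weighted kappa, chance-expected agreement, a confidence interval for agreement and any distinction between adjacent and opposite colours are not mentioned. No expected colour distribution is given for any group.

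**The concern.** Raw agreement depends on two things: how closely the methods track each other, and how unevenly people are spread over the colours. If nearly everyone is one colour in both methods, two unrelated instruments will still agree most of the time. If people are evenly spread, even closely related instruments disagree often, because many people lie near a cut-off. One raw threshold for all groups mixes the two effects. It also counts a red-green disagreement the same as a red-orange one.

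The module is meant to tell individuals where their own diet can improve. A group can meet 75% without the module distinguishing individuals at all. Another can miss it although the module ranks people well. Only the second is certain to receive the qualitative review, because the sole trigger is raw agreement below 75%.

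**Working it through.** **Inputs.** From the documents: the 75% goal, three categories, the same cut-offs for both methods (Sections 2, 6 and 8), and 200 participants as the minimum target (Section 4). The 75% is a chosen threshold with no derivation, so there is no plan figure to reproduce. Assumed, because the documents are silent: the colour shares (a range is shown), equal shares in both methods, and bivariate-normal underlying intake with correlation r.

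**Formulas.**
- Chance agreement: Pe = Σ pᵢqᵢ, which is Σ pᵢ² when shares are equal.
- Unweighted kappa: (Po − Pe)/(1 − Pe).
- Po at a given r: the sum of the diagonal of the 3x3 table obtained by cutting the bivariate normal at the assumed shares.
- Chance of meeting the goal: P(X ≥ 150), with X binomial (200, Po).

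**Examples.** For 86/9/5, Pe = 0.7396 + 0.0081 + 0.0025 = 0.750. For an even split, 75% agreement means kappa = (0.75 − 0.333)/(1 − 0.333) = 0.63. For 85/10/5 it means (0.75 − 0.735)/(1 − 0.735) = 0.06.

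| Shares (%) | Chance agreement | Kappa at exactly 75% | r needed for 75% | P(at least 75%) with no association, n = 200 |
|---|---|---|---|---|
| 33/33/33 | 33.3% | 0.63 | 0.91 | about 0 |
| 70/20/10 | 54.0% | 0.46 | 0.79 | about 0 |
| 80/15/5 | 66.5% | 0.25 | 0.55 | 0.6% |
| 85/10/5 | 73.5% | 0.06 | 0.17 | 35% |
| 86/9/5 | 75.0% | 0.00 | 0 | 54% |
| 90/7/3 | 81.6% | −0.36 | none | 99% |

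**The even split at high correlation.**
- r = 0.80: expected agreement 64.9%, chance of meeting the goal 0.1%.
- r = 0.85: 69.0% and about 4%.
- r = 0.90: 74.2% and 44%, with kappa (0.742 − 0.333)/0.667 = 0.61.

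**Precision.** The 95% half-width around 75% is 1.96 × √(0.75 × 0.25/n). This is 6.0 points at n = 200 and 10.4 points at n = 67, a third of the sample. A point estimate near 75% therefore says little about which side of the goal the group lies on, especially within subgroups.

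**The case against.** The strongest reply is that the overlap figure does not stand alone. Section 8 also plans correlations between the scores and, for every product group, between intakes in grams, whether or not 75% is reached. A group that met the goal with no association would show a near-zero correlation in the same set of analyses. This stands in part: the planned output would help expose an empty pass. But no threshold is attached to any correlation between Nutri+ and Compl-Eat, the gram results are described as mainly exploratory, and the correlations do not enter the trigger for qualitative review.

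Classification is also a sub-objective and a secondary outcome; the main objective is intake in grams. Missing the goal leads to review, not rejection. That is correct and limits the severity.

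Three stronger readings are tempting but not supported.
- A reader might infer that the plan will pass worthless groups and direct improvement work at the wrong ones. The documents give no colour shares. Chance alone reaches 75% only when one colour holds about 86% or more in both methods, and at 80/15/5 a correlation of about 0.55 is still needed. It could happen; whether and where is unknown.
- A reader might infer a contradiction with the reproducibility target of at least 0.75 in Section 2, since at r = 0.75 an evenly split group agrees with itself in only 61.4% of people. The two targets concern different comparisons, 0.75 is a minimum, and self-agreement at that correlation is 73% for 70/20/10, 80% for 80/15/5 and 84% for 85/10/5. There is no general clash.
- A reader might conclude that success should require both 75% raw agreement and a lower 95% limit of weighted kappa above 0.40. Under the same model with n = 200, this leaves the evenly split group at r = 0.85 passing only about 4% of the time. At r = 0.80 it passes about 51–53% of the time for 80/15/5, 35–37% for 85/10/5 and 19–20% for 90/7/3. It does not cure one fault and adds another.

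**Conclusion.** The point holds in a limited form. Exactly 75% raw agreement corresponds to a kappa of 0.63 in an evenly split group, 0.06 at 85/10/5 and below zero at 90/7/3, so the goal is not a common standard across groups. The chance-agreement figures assume equal shares in both methods; the correlations also assume bivariate-normal intake. Unequal shares would change the numbers but not the dependence on colour distribution. The number of the 21 groups affected cannot be determined from the documents. Severity is should-fix: the planned correlations give partial protection, and the consequence is a choice of groups for review within a sub-objective.

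**What to change.** Amend Section 8 before the data are analysed. For each product group report:
- the full 3x3 table;
- raw agreement with its 95% confidence interval;
- chance-expected agreement;
- linear-weighted kappa with its 95% confidence interval;
- agreement within each colour;
- the percentage in opposite colours (red by one method, green by the other).

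Keep the 75% goal, but interpret it beside these figures. Extend the trigger for qualitative review: besides raw agreement below 75%, review a group when its agreement is not clearly above the chance-expected value, for example when the 95% interval of weighted kappa includes zero. Where a group misses 75% but weighted kappa is high, say so, so that the miss is not read as poor tracking. Do not make success conditional on both 75% and a kappa lower limit above 0.40.

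The cost is SAP wording and standard output, with no new data. Some skewed groups will be sent for review, and kappa will be imprecise in them, which is why the table, chance-expected agreement and per-colour agreement should stand beside it.
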